A meta-analysis of 22 studies of 8,840 HEU and 20,372 HUU demonstrated 70% increased mortality in HEU exposed to untreated maternal HIV; mortality risk in HEU versus HUU declined in magnitude but remained elevated following expansion of PMTCT⁵². Another meta-analysis of 12 studies involving 5,074 HEU and 12,881 HUU estimated 20% and 30% increase risk of pneumonia and diarrhea in HEU, respectively⁵³. In a US study involving 2,404 HEU children and data from over 3.6 million HUU children in the Medicaid Analytic Extract database, HEU children had ~2-fold increased rate of hospitalization⁵⁴. HEU differ from HUU in gut microbiome, immune activation, and inflammatory markers, which in turn may alter growth or infectious morbidity⁵⁵⁻⁵⁸. HEU have recently been shown to have poorer lung function than HUU⁵⁹. These data suggest that common mechanisms following fetal HIV/ART exposure could drive diverse long-term outcomes in HEU, including mental health outcomes⁶⁰.

HEU have risk of poor mental health outcomes

There are limited data regarding mental health outcomes in HEU. Pediatric HIV (PHIV) infection has been associated with increased anxiety, attention deficits, impulsivity, hyperactivity and depression in high- and middle-income settings. Some studies have noted high prevalence of behavioral problems, often with similar prevalence in HEU and PHIV⁶¹. In a comparison of PHIV, HEU and HUU from Uganda, children aged 6-18 years old were assessed for psychosocial adjustment; HEU were noted to have significantly lower positive outlook and self-esteem than HUU⁶². Caregiver depressive symptoms were associated with child behavioral outcomes (poor executive function) among PHIV in a recent study³⁵. Similarly, mental health outcomes in HEU may be influenced by caregiver interactions, complicating ascertainment of the effect of fetal HIV/ART exposure.

Implications of fetal origins of mental illness among HEU

Because HIV is an incurable disease with high risk of substantial morbidity and mortality, ART both for maternal health and prevention of infant HIV is required. Recent studies on DTG and neural tube defects and isoniazid prophylaxis in pregnancy illustrate the complexities of optimizing maternal/infant outcomes^{49,50,63}. The time delay HOPE study protocol

Version 1.3

July 21, 2020

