Neurodevelopmental outcomes: MDAT scores (social, fine motor, gross motor, and language) will be analyzed as z-scores and descriptive statistics for each domain will be summarized and compared between HEU and HUU using linear regression, with clustering for site (Table 6). MDAT scores at baseline (6 weeks) and changes in MDAT scores during follow-up will be compared between HEU and HUU and among HEU by maternal VL detection in pregnancy, and by pre-conception versus later ART, and ART regimen (EFZ versus DTG-backbone) using univariate and multivariate linear regression. Prevalence of high risk for **ASD** as assessed by M-CHAT R/F and **hearing loss** will be compared for HEU and HUU using multivariate generalized linear models (GLM) with log link and binomial family for relative risk estimation, overall and stratified in HEU and HUU.

Table 6. Outcomes and analytic approach for longitudinal cohort		
Outcome variable	Comparisons	Analytic approach
Primary outcome: Neurodevelopmental outcomes MDAT	HEU vs. HUU Maternal VL Pre-conception ART EFZ vs. DTG	Linear regression for social, gross motor, fine motor, and language z-score GLM
ASD prevalence or hearing loss		
Secondary outcomes		
Growth (WAZ, WHZ, HAZ, HC at 12, 24, 48 months) Prevalence of underweight, wasting and stunting Growth trajectory (change in HAZ)	HEU vs. HUU Pre-conception ART EFZ vs. DTG	Linear mixed effects models
Hospitalization	HEU vs. HUU	Cox regression
Severe infections	HEU vs. HUU	Cox regression
Mortality	HEU vs. HUU	Cox regression

Growth outcomes: We will compare growth outcomes between HEU and HUU and among HEU by maternal VL detection in pregnancy, maternal pre-conception ART, and by ART regimen. Growth will be converted to z-scores using WHO Anthro software and 12- 24- and 48-month median WAZ, WHZ, and LAZ and prevalence of underweight, stunting and wasting will be compared. In addition, growth trajectory will be compared. Missing values will be imputed using Markov chain Monte Carlo procedures. Loess curves will be created to plot growth trajectory over time for WAZ, WHZ, and LAZ. Linear mixed-effects models will be used to determine correlates of growth (separately for WAZ, WHZ, and LAZ) in univariate and multivariate models.

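### Imputation is written only for the secondary growth outcomes and has no limit at death, while the primary MDAT outcome gets ordinary regression that by default drops absent children

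*Protocol*

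**What the plan says.** All of the following is in the protocol.

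- **Growth (12.c.vii, Growth outcomes; secondary in Table 6).** "12- 24- and 48-month median WAZ, WHZ, and LAZ and prevalence of underweight, stunting and wasting will be compared". The same paragraph says "Missing values will be imputed using Markov chain Monte Carlo procedures" and then "Linear mixed-effects models will be used to determine correlates of growth (separately for WAZ, WHZ, and LAZ) in univariate and multivariate models". No limit on the imputation is given.
- **MDAT (12.c.vii, Neurodevelopmental outcomes).** Table 6 has "Primary outcome: Neurodevelopmental outcomes MDAT". The domain z-scores are "compared between HEU and HUU using linear regression, with clustering for site", and "MDAT scores at baseline (6 weeks) and changes in MDAT scores during follow-up will be compared between HEU and HUU", again by linear regression. No missing-data step is attached.
- **Schedule (12.c.vi, summary table for Aim 1).** MDAT and anthropometry are done at enrollment and at every 6-monthly visit to month 48, nine visits in all. The same section has caregiver PHQ-9 at every visit.
- **Death.** Mortality is its own secondary outcome in Table 6. The morbidity and hospitalization analyses censor at death and at loss to follow-up. The Background (section 8) says that the excess mortality in HEU became smaller after PMTCT expanded but did not disappear.
- **Attrition (12.d.vii, effect-size table).** A 20% attrition column raises the detectable MDAT difference from 0.13 to 0.14 at SD 1.0. Attrition is not split by group, and the limitations in section 16 do not mention it.

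**The concern.** Two things are fixed badly in what is written.

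First, the imputation sentence taken literally fills a 48-month length or weight z-score for a child who died before month 48. Such a value describes nothing. If mortality is higher in HEU, there will be more of these values in that group.

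Second, the protection against dropout is in the wrong place. Growth gets imputation and, in part of its analysis, mixed models that already use every available visit. The primary outcome has the same repeated measurements but gets a method that makes no use of an absent child's earlier scores. At stake is the HEU versus HUU contrast at later visits, including the 4-year neurodevelopmental question in Aim 1a. Selective loss there could move the estimate by a sizeable part of the difference that the cohort is designed to detect.

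**Working it through.** **1. The plan's own figure.** Inputs from the effect-size table: 1000 per group, 20% attrition (800 per group), SD 1.0, power 80%, alpha 0.05. Sidedness is not stated; two-sided reproduces the table.

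Detectable difference = (1.960 + 0.842) × SD × √(2/n).

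- n = 1000: 2.802 × 0.0447 = 0.125 (stated 0.13)
- n = 800: 2.802 × 0.0500 = 0.140 (stated 0.14)

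The 0.14 reproduces with the sample size as the only change. Attrition is therefore treated as lost precision, with no allowance for selection.

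**2. Shift from selective loss in an attenders-only comparison of levels.** Let p be the share lost and g the amount by which lost children would have scored below retained children in the same group. The retained mean exceeds the full-group mean by p × g. The HEU deficit is therefore understated by

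p(HEU) × g(HEU) − p(HUU) × g(HUU).

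The documents give 20% overall. The gaps g are assumptions. Power = Φ(observed deficit / SE − 1.96), with SE = √(2/800) = 0.05 and a true deficit of 0.14 SD.

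| Loss HEU / HUU | Gap HEU / HUU (SD) | Shift (SD) | Observed deficit | Power |
|---|---|---|---|---|
| 20% / 20% | equal | 0 | 0.14 | 80% |
| 20% / 20% | 0.3 / 0.1 | 0.20 × 0.2 = 0.04 | 0.10 | 52% |
| 20% / 20% | 0.5 / 0.1 | 0.20 × 0.4 = 0.08 | 0.06 | 22% |
| 20% / 20% | 0.25 / 0 | 0.20 × 0.25 = 0.05 | 0.09 | 44% |
| 20% / 20% | 0.1 / 0.5 | 0.20 × (−0.4) = −0.08 | 0.22 | deficit exaggerated |
| 25% / 15% | 0.5 / 0.5 | 0.10 × 0.5 = 0.05 | 0.09 | 44% |

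The last row uses SE = √(1/750 + 1/850) = 0.050. Relative to 0.14, shifts of 0.04 and 0.08 are 29% and 57%.

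**3. Which MDAT contrasts this touches.** The 6-week comparison precedes any dropout and is unaffected. In change scores, a stable difference in level between lost and retained children cancels, so g would have to be a gap in change. The figures above apply to MDAT levels at later visits.

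**4. Size of the post-death problem.** The documents give no mortality rate for this cohort. Assume 4-year mortality of 1% to 5% in HEU and 0.6% to 3% in HUU, with imputed values 0.5 to 1.0 SD below those of survivors. The between-group shift is (difference in mortality) × g: from 0.004 × 0.5 = 0.002 SD to 0.02 × 1.0 = 0.02 SD. This is small beside the effect of loss to follow-up.

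**The case against.** The strongest reply is that the protocol nowhere restricts MDAT to attenders. It names linear regression and is silent on missing scores. A statistical analysis plan, which is not among the documents at hand, may settle the matter, so the silence alone is not a fault. That is right. What remains is what the protocol does state: an unrestricted imputation rule for a secondary outcome, and for the primary outcome a method whose default discards absent children.

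A reader might go further and infer that dropout will hide an HEU deficit. The documents do not support that. The dropout gaps have no source in them, attrition is not split by group, equal loss with equal gaps gives no shift, and the reverse pattern exaggerates the deficit. Adjustment for maternal depression, sociodemographic factors, birthweight and growth would also absorb some of the selection.

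A reader might also infer a serious distortion of growth from deaths, citing the 70% excess mortality in the Background. That figure concerns untreated maternal HIV. Section 16 says that all HEU mothers in this cohort began ART before or during pregnancy, and infants must be healthy at enrollment. Only the milder statement, that some excess persisted after PMTCT expansion, applies here. It is also fair that the authors censor at death in the morbidity analyses, so they may intend the same for growth. The growth paragraph does not say so.

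Finally, it might seem natural to extend the same imputation to ASD, hearing and SDQ. That is debatable. ASD and hearing loss are rare binary screens (2% and 1% assumed in HUU), and SDQ starts only at month 36, so a child lost earlier has no prior SDQ score to draw on.

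**Conclusion.** The point holds in a limited form. As written, growth values would be created for children who have died, and the primary outcome is less protected against dropout than a secondary one although it has the same nine repeated measurements. The possible bias in the MDAT difference at later visits is 0.04 to 0.08 SD against a detectable 0.14 SD. This rests on assumed gaps of 0.3 to 0.5 SD (HEU) and 0.1 SD (HUU) at 20% loss, and on MDAT being regressed in attenders, which is the default reading and not stated text. The direction is not known in advance and the shift may be zero. Post-death imputation matters for the meaning of the growth results much more than for their size. The change should be made because it is cheap and uses data already collected.

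**What to change.** 1. In Growth outcomes, restrict imputation to visits scheduled while the child was alive, and report the number of deaths by group beside each growth and MDAT time point.
2. For MDAT, replace visit-by-visit regression as the main analysis with a linear mixed model over all visits, as the plan already has for growth. Alternatively, use multiple imputation with earlier MDAT scores, LAZ, maternal PHQ-9, site and HEU status in the imputation model.
3. Keep the attenders-only regression as a sensitivity analysis.

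The cost is a few lines of text and modest programming. No new data, visits or sample size are needed, and the stated detectable differences do not change. Both MDAT options rely on missing at random, so they correct only selection explained by recorded data. A further sensitivity analysis that lets lost children score lower by a different amount in each group would show how far that assumption matters.

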Design	
This study will provide rigorous epidemiologic evidence regarding the influence of fetal exposure to HIV and ART on developmental and mental health outcomes from infancy to adolescence using the following study designs: Longitudinal cohort study, cross sectional assessments and costing and implementation surveys. Accrued data will be disseminated in a stakeholder workshop conducted in the last year of the study.
 
To do this we will enroll a longitudinal cohort of HIV exposed uninfected (HEU) and HIV uninfected (HUU) infants and follow them up 6 monthly with extended follow-up to 4 years. Assessments will include growth, hearing and neurodevelopment (Aim 1a) and telomere length (Aim 1b).
 
In Aim 2, we will utilize a cross-sectional study design to pilot test mobile screening strategies to detect neurodevelopmental and mental health outcomes in HEU (Aim 2a). Pilot results will inform the implementation of a larger population based cross-sectional assessment of HEU outcomes (Aim 2b).
 
In aim 3, we will estimate the cost of the screening strategies and convene a stakeholder workshop to review data regarding programmatic integration of HEU screening.

Population	
Aim 1: HEU and HUU infants age 6 weeks and their mothers
 
Aim 2: HEU and HUU children and adolescents age 3-18 years and their caregivers
 
Aim 3: Abstracted records of cost information, Stakeholders in pediatric and adolescent health, health care workers (HCW), policy makers

Sample size	
Aim 1: 2000 mother-infant pairs, 1000 HEU and 1000 HUU
 
Aim 2: Pilot phase: 200 HEU and 200 HUU and their caregivers, Population based assessments: 4000 caregiver-child HEU pairs, 400 caregiver-child HUU pairs
 
Aim 3: 25-50 HCW, policy makers and stakeholders in pediatric health

Study sites:	
Aim 1: 5 public sector maternal and child health (MCH) clinics, 2 in urban Nairobi (Mathare, Kenyatta National Hospital) and 3 rural MCH clinic sites (Homa Bay, Kisumu, and Rachuonyo).
 
Aim 2: Pilot phase: Rachuonyo sub-county hospital. Population based assessments: 100 large HIV care clinics throughout Kenya
 
Aim 3: Workshop will be concerned in Nairobi/Western Kenya

Study Duration:	5 Years

8. Background

Maternal HIV and antiretroviral exposure may be potential fetal determinants of mental health

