Screening for child mental health conditions. The Strengths and Difficulties Questionnaire¹³¹ is a 25-item scale widely used as a screening tool for mental health in numerous LMIC settings¹³², including SSA¹³³. The SDQ will be used beginning at age 3. The SDQ includes 4 difficulty scales (emotional symptoms, conduct problems, hyperactivity/inattention, and peer relationship problems) and a scale for prosocial behavior. The Strengths and Difficulties Questionnaire¹³¹ is a 25-item scale widely used as a screening tool for mental health in numerous LMIC settings¹³², including SSA¹³³. The SDQ will be used beginning at age 3. The SDQ includes 4 difficulty scales (emotional symptoms, conduct problems, hyperactivity/inattention, and peer relationship problems) and a scale for prosocial behavior. SDQ scales had good internal consistency in African studies¹³⁵⁻¹³⁹, although the hyperactivity/inattention scale has performed less well¹³⁸. Poor SDQ scores correlated with expected demographic characteristics in South Africa and Uganda¹³⁷. A z-score corresponding to the 80th-90th and >90th percentiles have been considered borderline and indicative of 'caseness'¹³⁶, and will prompt further screening.

Hearing: We will use combined otoacoustic emission (OAE) and auditory brainstem response (ABR) screening tests to assess hearing. Infants will be screened at 6 weeks using OAE and referred for ABR if they screen positive. At age 3 and 4 years, we will use a smart phone based hearing screen (Hearscreen TM) to assess hearing. These tests are non-invasive and does not involve input of energy into the body.

Summary table for aim 1 data collection

	Enrollment	Month 6	Month 12	Month 18	Month 24	Month 30	Month 36	Month 42	Month 48
Consent	X								
Locator data	X	X	X	X	X	X	X	X	X
Medical history	X	X	X	X	X	X	X	X	X
Anthropometry	X	X	X	X	X	X	X	X	X
MDAT	X	X	X	X	X	X	X	X	X
SDQ							X	X	X
ASD screen				X	X				X
Hearing screen	X						X		X
DBS	X		X		X		X		X

vii. Sample size determination & data analysis

For **all analyses**, *a priori* cofactors of interest in the multivariate analysis include household sociodemographic factors, birthweight, preterm birth, maternal depression, infant sex, maternal education, and infant/child LAZ. Collinearity will be examined using standard error assessments and multivariate models will include non-collinear variables associated with growth in univariate model ($p < 0.05$).

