Mortality, infectious morbidity, and hospitalizations: Cox regression will be used to compare survival of the HEU and HUU cohorts and to determine predictive factors for mortality overall and stratified by HEU/HUU. During the 4-year follow-up period for the aim 1 cohort, incidence of hospitalization, severe pneumonia, and diarrhea will be calculated and compared between HEU and HUU cohorts as number of events over person-time of follow-up with censoring for mortality and loss to follow-up. Predictors of first morbidity (separate analyses for pneumonia, severe diarrhea, and hospitalizations) will be identified using Cox proportional hazards regression with censoring for mortality and loss to follow-up.

Analysis: We will compare MDAT social, motor and language scores and prevalence of ASD between HEU and HUU and among HEU by maternal VL detection in pregnancy, maternal pre-conception ART, and by ART regimen. The percentage of normal, borderline and high scores on the SDQ will be calculated for the domains: emotional problems, conduct problems, hyperactivity, peer problems, and prosocial behavior and for total difficulty. Univariate and multivariate logistic regression will be used to determine whether HEU vs. HUU is associated with higher likelihood of high scores on SDQ domains overall. Among HEU, we will assess influence of maternal VL, ART, and regimen. Multivariate analyses will be adjusted for maternal sociodemographic factors and depression and infant birthweight and growth.

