Cognitive outcomes. Cognitive assessments will be done using NIH Toolbox. The battery will include the tests Dimensional Change Card Sort Test, Flanker Inhibitory Control and Attention Test, List Sorting Working Memory Test, Pattern Comparison Processing Speed Test, and Picture Sequence Memory Test, which evaluate working memory, attention, processing speed, and other aspects of executive functioning. The NIH Toolbox has been validated for US children and was recently adapted through a rigorous process involving translation and backtranslation for Kenya, including translation to Dholuo and Kiswahili.

The table below summarizes the tools, age-group they are used in, screening time and domains or disorders they test.

Tool	Age-group	Time (minutes)	Types	Domains/Disorder
MDAT	0.6-5	30	Screening	Gross motor, fine motor, language, social
HearScreen TM	3+	5	Screening	Hearing
NIH Toolbox	6-17	25-30	Screening	working memory, attention, processing speed, executive functioning
Strengths and difficulties questionnaire (SDQ)	3-16 & caregivers	10	Screening	Emotional symptoms, conduct problems, hyperactivity/inattention, peer relationship problems
SNAP-IV	6-12	5-10	Screening	ADHD
PHQ-9	>16 & caregivers	3	Screening	Depression
MINI-KID	6-17	10	Diagnostic	Common psychiatric conditions
MINI	18	10	Diagnostic	Common psychiatric conditions
School performance	>10	1	NA	National exam results Parental report

vii. Sample size determination & data analysis

Effect size calculations: For comparisons of z-scores in MDAT or NIH-toolkit scores, we will be able to detect differences of 0.13-0.18 assuming a standard deviation of 1.0 or 1.4, 80% power and alpha of 0.05 in Aim 1 cohort (Table 10). In the cross-sectional cohort, 2- to 3-fold differences will be detectable, in diagnoses such as depression and ADHD. To detect smaller differences, more HUU could be enrolled in some age-strata based on pilot feasibility.

R61/R33 Aim 1 cohort	Effect detectable (no attrition)		Effect detectable (20% attrition)	Assumptions
Difference in z-score for MDAT	0.13 (SD=1.0)	1000 HEU:1000 HUU	0.14 (SD=1.0)	Standard deviation = 1.0-1.4 ¹⁰⁵
	0.18 (SD=1.4)		0.20 (SD=1.4)	
Difference in ASD prevalence	2.2%	1000 HEU:1000 HUU	2.5%	HUU ASD 2%
	3.3%	500 DTG: 500 EFZ	3.8%	
Difference in SDQ+ prev.	5.2%	1000 HEU:1000 HUU	5.9%	HUU SDQ+ 20%
	7.5%	500 DTG: 500 EFZ	8.5%	
Difference in hearing loss	1.7%	1000 HEU:1000 HUU	2.0%	HUU 1%
	2.7%	500 DTG: 500 EFZ	3.1%	
Difference in TL	0.18	500 HEU: 500 HUU		SD=1.0

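### The Aim 1 SDQ is measured at three visits per child, but the protocol names a logistic model for independent records and fixes no visit; a child-clustered analysis of all three would gain power at little cost

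*Protocol*

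**What the plan says.** Three parts of the protocol bear on this point.

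- **Schedule (section 12.c.vi).** The text on child mental health screening says "The SDQ will be used beginning at age 3". The summary table of Aim 1 data collection marks the SDQ at months 36, 42 and 48, so a child who completes follow-up has three results.
- **Analysis (section 12.c.vii, Analysis paragraph).** "Univariate and multivariate logistic regression will be used to determine whether HEU vs. HUU is associated with higher likelihood of high scores" on the SDQ domains. The paragraph states no visit, no rule for combining visits and no clustering on child. The SDQ is not listed in Table 6.
- **Sizing (section 12.d.vii, effect-size table).** The row "Difference in SDQ+ prev" gives 5.2% for 1000 HEU against 1000 HUU, with 20% SDQ-positive in HUU, and 5.9% in the column headed "Effect detectable (20% attrition".

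For growth, by contrast, section 12.c.vii names assessment months and a repeated-measures model: "Linear mixed-effects models will be used to determine correlates of growth". For MDAT it names "using linear regression, with clustering for site", which deals with dependence within site but not within child.

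**The concern.** Results on the same child at three ages will be correlated. Ordinary logistic regression assumes independent records, so it suits one result per child. The protocol schedules three and does not say which is used.

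That leaves two main readings. With one visit, the analysis is sound but two scheduled assessments add nothing to the comparison, and the choice of visit stays open until the data are seen. With all visits entered as they stand, the standard errors would be too small.

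The SDQ is the only general child mental health screen in the Aim 1 cohort, autism being screened separately. A false signal of an HEU excess, or a real one missed, would therefore matter for the mental health part of that aim.

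**Working it through.** **Inputs from the protocol**
- "2000 mother-infant pairs, 1000 HEU and 1000 HUU" (study summary table).
- SDQ-positive in HUU 20%; detectable difference 5.2 points, or 5.9 with 20% attrition, i.e. 800 per group (effect-size table).
- "80% power and alpha of 0.05 in Aim 1 cohort" (section 12.d.vii). That sentence concerns z-scores; I apply the same values to the SDQ row and take the test as two-sided.
- m = 3 SDQ visits per child (Aim 1 schedule).

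**Assumption not in the protocol**
- Within-child correlation ρ of SDQ-positive status: 0.3, 0.5 and 0.7.

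**Step 1: reproduce the table with one record per child.** Power for two proportions, pooled variance under the null, no continuity correction:

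Power = Φ{ [d√n − 1.96√(2p̄(1−p̄))] / √(p₁(1−p₁) + p₂(1−p₂)) }

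With n = 1000, p₁ = 0.20, p₂ = 0.252, d = 0.052 and p̄ = 0.226:
- d√n = 1.644
- 1.96√(2 × 0.226 × 0.774) = 1.159
- denominator √(0.1600 + 0.1885) = 0.590
- (1.644 − 1.159)/0.590 = 0.82, so power = 79.4%

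Solved for 80% power, the detectable difference is 5.24 points at 1000 per group and 5.89 at 800 (protocol: 5.2 and 5.9). The DTG against EFZ entries also reproduce: 7.53 at 500 and 8.48 at 400 (protocol: 7.5 and 8.5). The table is therefore a one-record-per-child calculation.

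**Step 2: three visits, clustered on child.** Design effect DE = 1 + (m − 1)ρ = 1 + 2ρ. Effective number per group = 3 × 1000/DE, put into the Step 1 formula. The share of the three-visit information kept by one visit is DE/3.

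| ρ | DE | Effective n per group | Power at 5.2 points, one visit | Power at 5.2 points, three visits | Information kept by one visit |
|---|---|---|---|---|---|
| 0.3 | 1.6 | 1875 | 79.4% | 96.8% | 53% |
| 0.5 | 2.0 | 1500 | 79.4% | 92.6% | 67% |
| 0.7 | 2.4 | 1250 | 79.4% | 87.5% | 80% |

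With 800 per group and 5.9 points, power is 80.2% for one visit, and 97.0%, 93.1% and 88.1% for three. These figures assume the same HEU–HUU difference at each visit and all three results for every retained child.

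**Step 3: all records in the named model, correlation ignored.** The naive variance is too small by the factor DE, so

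Type I error = 2[1 − Φ(1.96/√DE)]

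At ρ = 0.5: 1.96/√2 = 1.386, giving 16.6%.

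| ρ | Formula | Simulation, naive | Simulation, clustered on child |
|---|---|---|---|
| 0.3 | 12.1% | 12.3% | 4.8% |
| 0.5 | 16.6% | 16.7% | 4.5% |
| 0.7 | 20.6% | 20.6% | 5.1% |

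The simulation used 4000 data sets per row, 1000 children per group, three visits and 20% prevalence in both groups. A type I error of exactly 15%, three times nominal, needs ρ of about 0.43.

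**The case against.** The strongest reply is that the sizing and the named test already agree. The table is built on one record per child, logistic regression on one record per child is valid as regards within-child correlation, and it delivers the power that was planned. Which visit to use, and how to treat correlated visits, is often settled in a statistical analysis plan, and none is shown here. Averaging over three ages also changes the question from a difference at one age to an average difference. All of this stands, and it is why the point is an improvement and not an error.

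A reader might infer two stronger claims, and the documents support neither.

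- *That the false-positive rate triples.* The protocol nowhere says that the visits will be pooled as independent records, and its sizing points to one record per child. Even under pooling, the factor depends on a correlation that the protocol does not give: it runs from 2.4 (12.1/5) to 4.1 (20.6/5) over ρ of 0.3 to 0.7.
- *That using one visit discards most of the power.* One visit gives the planned power of about 80% and keeps 53% to 80% of the three-visit information. Counting two of three records as lost overstates the loss, because correlated records partly repeat one another.

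The reply does not remove the mismatch. The protocol commits to a model that assumes independent records for an outcome scheduled three times, and names no visit that would make the two fit.

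**Conclusion.** The point holds as a modest, inexpensive improvement. The schedule, the named model and the sizing are not joined up, because the visit is not fixed. A single-visit analysis would be valid and would meet the plan. Against it, a child-clustered analysis of the three scheduled visits would raise power at 5.2 points by about 8 to 17 percentage points (87.5 − 79.4 to 96.8 − 79.4). That gain rests on the assumed correlation range, a constant difference and complete visits, and it shrinks if SDQ visits are missed or the difference changes with age. The inflated type I error is conditional on an analysis that the protocol does not state; it is a reason to close that reading off, not a fault shown in the plan.

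**What to change.** In the Analysis paragraph of section 12.c.vii, state that SDQ-positive status at months 36, 42 and 48 is analysed in one model with visit as a category, by GEE with robust variance clustered on child. The test is of the HEU effect averaged over visits, and the month-48 difference is reported as secondary.

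As a minimum, keep logistic regression and name one visit in advance, for example month 48. That matches the sizing table.

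A log link, as already chosen for autism risk and hearing loss in Aim 1, would put the SDQ on the relative-risk scale too. It is optional and separate from this point.

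The cost is a wording change and slightly more analysis work, with no new data. The drawback of the full change is that the month-48 contrast on its own is no longer the main SDQ result.
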